### **Screening Phase**

The Screening Phase is defined from the Screening Visit up to, but not including Visit 1. This includes any Re-screening Visits that are conducted.

Study specific version: 1.0  
Study specific version Date: 31-May-17

### **Active Trial Phase**

The active trial phase is defined as the trial phase starting with and including Visit 1 and ending with and including EAP (End of active trial phase) (V3 + 28-35 days).

### **End of Active Trial Phase (EAP)**

EAP is defined as the last visit of the active trial phase.

### **Follow-Up Trial Phase**

The Follow-Up trial phase is defined as the phase starting after EAP visit and includes the Follow-up visits (FU1 and FU2).

### **Eligible Subjects**

A subject is eligible if the screening question “Is subject eligible and willing to continue?” is answered with “Yes” and there are no subsequent substantial protocol deviations that affect the eligibility of the subject at Visit 1 prior to randomization.

### **Subjects Receiving Both Vaccinations**

A subject is considered as having received both doses of trial vaccination per the randomized group assignment if a date of drug administration is given for the vaccination at Visit 1 and for the vaccination at Visit 3, and no major vaccine preparation or administration deviation is recorded.

### **Treatment-Emergent Adverse Events (TEAE)**

An Adverse Event (AE) with onset either on the day of a vaccination, but after the vaccination or within the 28 days following a vaccination. Note that serious AEs are also considered treatment-emergent after 28 days (see below).

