##### 8.1.2.1 Unsolicited AEs

Unsolicited AEs are defined as AEs observed by the subject/investigator or which are not pre-listed on the memory aid card. AEs (e.g. feeling of ill-health, subjective symptoms and objective signs, intercurrent diseases, accidents, etc.) observed by the investigator and/or reported by the subject must be recorded in the eCRF regardless of the assessment of causality in relationship with the IMP/MP.

After the first vaccination, abnormal laboratory values assessed as being clinically significant by the investigator are to be documented as AEs. In addition, after first vaccination, abnormal laboratory values fulfilling the Grade 3 or Grade 4 criteria according to the toxicity scale ([Appendix 1: Toxicity Scale for Laboratory Values](#)) are to be documented as AE in the eCRF, regardless of whether they are considered clinically relevant or not. For lab values fulfilling the Grade 3 or Grade 4 criteria, the decision to repeat the labs is left at the discretion of the PI. Toxicity grade and seriousness of an AE will be assessed separately, i.e. a Grade 3 or Grade 4 AE will not automatically be regarded as serious.

The investigator should ask the subjects if they have experienced any AEs since their last visit. All intercurrent diseases reported by the subject need to be recorded by the investigator in the appropriate section of the eCRF.

Any adverse events starting during the screening phase, i.e. after informed consent is given but before the first vaccination, are considered as pre-treatment adverse events.

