### Assessment of Causality

The relationship between the occurrence of an AE and the IMP will be assessed using the categories presented below. For expedited reporting and all other purposes, the categories “none” and “unlikely” will represent no evidence or argument to suggest a causal relationship, while “possible”, “probable” and “definite” will be seen to convey that there is evidence or argument to suggest a causal relationship. Following worst case scenario all AEs without a causality assessment from the investigator will be classified as “possible”.

- None** The time interval between administration of the IMP and the occurrence or worsening of the AE rules out a relationship, and/or another cause is established and there is no evidence of a (concomitant) causal connection with or worsening caused by the IMP.
- Unlikely** The time interval between administration of the IMP and the occurrence or worsening of the AE makes a causal relationship unlikely, and/or the known effects of the IMP or substance class provide no indication of a (concomitant) causal connection with or worsening caused by the IMP and there is another cause which serves as an adequate explanation, and/or although the known effects of the IMP or substance class make it possible to derive a plausible causal chain with regard to a (concomitant) causal connection or worsening, however, another cause is considerably more likely, and/or another cause of the AE has been identified and a (concomitant) causal connection with or worsening caused by the IMP is unlikely.
- Possible** A plausible causal chain with regard to a (concomitant) causal connection with / worsening of the AE can be derived from the pharmacological properties of the IMP or substance class. However, other approximately equally likely causes are known, or although the pharmacological properties of the IMP or substance class provide no indication of a (concomitant) causal connection with / worsening of the AE, there is no other known cause which provides an adequate explanation.

Probable	The pharmacological properties of the IMP or substance class, and/or the course of the AE after discontinuation of the IMP and possible subsequent re-exposure, and/or specific findings (e.g. positive allergy test or antibodies against the IMP / metabolites) suggest a (concomitant) causal connection with / worsening of the AE resulting from the IMP, however another cause cannot completely be ruled out.

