 New SAEs, new AEs indicating a respiratory tract infection and changes to AEs/SAEs ongoing at the previous visit only.

 At Screening Visit, a serum pregnancy test must be performed. At all other visits, a urine pregnancy test is to be performed.

 Additional safety measures can be taken at any other trial visit or at unscheduled visits, if clinically indicated.

 Approximate amounts of single blood draws: Safety lab: 19 mL (at V2, V4, FU1 and FU2; if applicable), including Haematology (3 mL), serum chemistry (including pregnancy test; 8 mL), virology (Hepatitis B and C, HIV; 5 mL); Safety lab 22 mL (at SCR), including all above plus HbA1c (3 mL; if applicable); Troponin I: 3 mL; serum collection (antibody testing): 9 mL; PBMC collection (T cell collection): 64 mL. Maximal total amount of blood taken/subject: up to 176 mL (642 mL for subjects in the subgroup).

Study specific version: 1.0  
Study specific version Date: 31-May-17

 The memory aid should be completed daily for an 8-day period (Day 0 to Day 7), starting with the day of vaccination. If symptoms are ongoing after Day 7, temperature/symptom measurements should continue each day until resolved and the last day of the symptom and maximum intensity will be recorded on the memory aid.

 The entries on the memory aid card need to be reviewed together with the subject.

 Only in the presence of symptoms indicating a respiratory infection at any timepoint after first vaccination, defined by any case of rhinorrhea, nasal congestion, pharyngitis, cough, wheezing (or increase in baseline wheezing), sputum production (or increase / change in nature of baseline sputum production) or new (or worsening of) shortness of breath. Subjects need to be instructed to return to the site within 3 days after start of symptoms.

 Subgroup only.

 Refer to Protocol Section 8.2.9 for Cardiac Assessment

 Nasal swabs will be taken from both nostrils.

 During the staggering phase, data from the memory aid need to be transferred to the Electronic Case Report Form (eCRF) immediately for SMT (Safety Monitoring Team) review and the memory aid card will be returned to the subject to complete entries for the remaining days.

 Visit VS (Staggering Visit) is only required for the subjects in the staggering phase, i.e. sentinel cohort and safety cohort; the target week is named as 0S.

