### **Pre-treatment Adverse Events**

AEs recorded after signing of the informed consent form but before the first administration of trial vaccine are considered pre-treatment AEs. These pre-treatment AEs will be presented in a subject listing.

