### **Unsolicited AEs**

Treatment-emergent unsolicited AEs in the active trial phase will be summarized by System Organ Class (SOC) and PT, and by vaccination period, and for overall. A similar table will be produced per subject.

Separate tables for related treatment-emergent unsolicited AEs, graded  $\geq 3$  treatment-emergent unsolicited AEs, and related graded  $\geq 3$  treatment-emergent AEs will be presented by vaccination period and overall.

The total number events and percentages of all treatment-emergent unsolicited AEs will be presented by intensity, relationship, and for related AE intensity.

Non-treatment-emergent AEs will be flagged and included in the listing only, but will not be included in the summary tables.

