### **Treatment Emergent Adverse Event (TEAE)**

A TEAE is an adverse event with an onset either on or after the day of the booster vaccination, or within the 28 days following the booster vaccination. Note that serious AEs are also considered treatment-emergent after 28 days (see below).

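### Both SAPs define a treatment-emergent AE by onset alone, so a narrow set of AEs that worsen after an injection reaches only a listing, and some second-dose worsening is shown under Period 1

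*SAP*

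**What the plan says.** The General Definitions of the main SAP make an AE treatment-emergent when it is one "with onset either on the day of a vaccination, but after the vaccination or within the 28 days following a vaccination". The booster SAP also ties the status to onset: "A TEAE is an adverse event with an onset either on or after the day of the booster vaccination". Neither definition has a clause for worsening.

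The protocol's causality scale (Section 8.2.5, Assessment of Causality) does cover worsening, in every category. For a rating of probable, for example, the evidence must "suggest a (concomitant) causal connection with / worsening of the AE resulting from the IMP".

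For AEs that begin before the first injection, protocol Section 8.1.2.1 states: "Any adverse events starting during the screening phase, i.e. after informed consent is given but before the first vaccination, are considered as pre-treatment adverse events". Main SAP Section 3.5.8 adds: "These pre-treatment AEs will be presented in a subject listing". For AEs that are not treatment-emergent, both SAPs say: "Non-treatment-emergent AEs will be flagged and included in the listing only, but will not be included in the summary tables".

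Main SAP Section 3.3.3 requires an unsolicited AE to start on or after the first vaccination, and assigns each AE to a vaccination period by its start. Protocol Section 8.2.5 grades each unsolicited AE by one maximum intensity.

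**The concern.** An investigator can correctly judge that an injection worsened an existing AE and rate that AE as related. The SAPs then classify it by the date on which it began. If that date lies before the injection, the related rating and the grade reached afterwards have no route into the treatment-emergent tables.

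The secondary safety endpoints include related AEs of Grade 3 or higher, and unsolicited non-serious AEs, within 4 weeks after each vaccination. Both are meant to show what follows an injection, and a vaccine-caused worsening belongs there. The omission also runs against the SAPs' own caution: a partly missing start date is treated as treatment-emergent on a worst-case principle, and a missing causality rating counts as related.

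**Working it through.** The plan gives no figure to reproduce. The check follows an AE with onset before an injection through the rules, assuming that the worsening stays on the original record.

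**Inputs.** The screening period is up to 28 days (protocol 4.2.1.1). Booster consent falls on days -28 to -1 (protocol 1.7). Dose 2 is given at V1 + 28-35 days (protocol 1.6). The TEAE window is 28 days (both SAPs).

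1. **Onset between consent and dose 1, worse after dose 1.** The AE is pre-treatment (protocol 8.1.2.1). It is not an unsolicited AE under main SAP 3.3.3, so the unsolicited part of the related Grade 3 summary cannot pick it up. Result: listing only.

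2. **Onset between booster consent and booster dose, worse after it.** The booster SAP also lists such AEs as pre-treatment. In addition, it defines treatment-related AEs as a subset of TEAEs, so this AE cannot count as related whatever the investigator decided. Result: listing only.

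3. **Onset more than 28 days after dose 1 but before dose 2, worse after dose 2.** The gap is at most 35 - 28 = 7 days (days 29 to 35). Main SAP 3.3.3 assigns the AE to Period 1 by start date, but 3.5.8 keeps any AE with onset later than 28 days after the previous vaccination out of the summary tables. Result: listing only. New respiratory-tract AEs are an exception, because the main SAP makes them treatment-emergent whatever their day of onset.

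4. **Onset within 28 days of dose 1, worse after dose 2.** The AE is treatment-emergent and is assigned to Period 1. It stays in the Period 1, Overall and per-subject tables at its single maximum grade. Result: not lost, but a grade reached after dose 2 is shown under dose 1 and is absent from the Period 2 rows.

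5. **Already captured.** SAEs from the first vaccination are treatment-emergent by definition. Solicited symptoms are scored afresh on a memory aid after each injection, with onset at the first score above 0 (main SAP 3.3.4). Grade 3 or 4 laboratory values after the first vaccination must be recorded as AEs (protocol 8.1.2.1). Symptoms present at screening are medical history (protocol 8.1.1), so a later change in health can be entered as a new AE.

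**Is the assumption about the record sound?** Protocol 8.1.2 asks for changes in health after consent to be documented as AEs, which could be read as requiring a new entry. No section says so for an AE that is already open.

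**Scale of one event.** Phase I had 0 related TEAEs of Grade 3 or higher in 3 x 18 = 54 vaccinated subjects (protocol Table 8). As an illustration only, the 95% Clopper-Pearson upper limit in a group of 80 is:
- 0 events: 1 - 0.025^(1/80) = 4.5%.
- 1 event: the p that solves (1-p)^80 + 80p(1-p)^79 = 0.025, which is 6.8%.

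This shows what one such event would do. It does not say that one is expected.

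**The case against.** The strongest reply is that very little is left. The AE must be non-serious, unsolicited and not a graded laboratory value. It must start in a short window, still be ongoing at the injection, worsen because of it, and not be re-entered. Eligibility excludes active cardiopulmonary and metabolic symptoms. Acute illness allows vaccination to be deferred, and upper respiratory illness calls for deferral until symptoms clear. The AE would still appear in a listing. All of this stands, and it limits the size of the point. It does not change the rule, which gives the wrong class for the events that remain.

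A reader might infer three stronger things, and the documents support none of them.

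- **All vaccine-caused worsening is lost from the summaries.** It is not: case 5 is captured, and case 4 is misplaced, not lost.
- **The one-dose versus two-dose safety comparison is biased by period assignment.** That comparison is between randomised arms (Group 2 with 1, Group 4 with 3). The Overall and per-subject tables keep a case 4 AE at its maximum grade whichever period it is filed under. Only the by-vaccination display of unsolicited AEs changes.
- **The schedule shows that worsening is kept on the old record.** The footnote on "changes to AEs/SAEs ongoing at the previous visit only" is attached only to the two follow-up visits, well outside the 28-day windows. It hints at practice but is not a rule for the active phase.

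**Conclusion.** The gap is real and narrow. Cases 1 to 3 are left out of the treatment-emergent, related and Grade 3 or higher summaries. Case 4 affects only which vaccination a grade is shown under.

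The finding assumes that a worsened AE stays on its original record. The eCRF completion rules might say otherwise, but they are not in these documents, and with up to 16 sites the outcome should not depend on local reading.

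The number of affected events cannot be derived, because the documents give no rate of pre-vaccination AEs or of worsening. It is probably small, and any count would be a guess. The change is still worth making: it is cheap, and the endpoint most exposed, related Grade 3 or higher AEs, may rest on very few events.

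**What to change.** In both SAPs, extend the TEAE definition to include an AE already present before a vaccination whose intensity grade rises on the day of that vaccination (after the injection) or within the following 28 days. In the eCRF guideline, require the worsening to be entered as a new AE with its own start date, grade and causality, and assign it to the period in which it worsened. In the booster SAP this also resolves the definition of related AEs, because the new record is itself a TEAE.

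If records can no longer be changed, add one table by treatment group of AEs ongoing at a vaccination that were assessed as related or reached Grade 3 or higher.

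The cost is one sentence in each SAP, one guideline line and one programming flag, or one extra table under the fallback. TEAE counts may rise slightly.

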### **Serious Adverse Events**

All Serious Adverse Events (SAEs) from first vaccination to last follow-up visit are considered as treatment-emergent regardless of the day of onset.

### **AEs related to respiratory tract infections**

New AEs related to respiratory tract infections will be assessed and documented at all trial visits, including the FU Visits and are considered as treatment-emergent regardless of the day of onset.

### **Adverse Drug Reaction**

An AE with either a ‘possible’, ‘probable’, ‘definite’ ‘unknown’ or ‘missing’ relationship to the vaccine (which means: “causally related”).

### **Nominal Titer**

The MVA-BN-RSV (Respiratory Syncytial Virus) vaccine is formulated at a nominal titer of  $5 \times 10^8$  Inf.U per dose (0.5 mL). The actual titer will be determined in stability testing.

Study specific version: 1.0  
Study specific version Date: 31-May-17

**Table 1: Detection Limits (DL)**

| Test  | Detection Limit (DL)       | Negative values reported                              |
|---|----------------------------|---|
| PBMC RSV-specific IFN- $\gamma$ ELISPOT (pool F, G(A), G(B), M2, N or RSV virus)
PBMC RSV-specific IL-4 ELISPOT (pool F, G(A), G(B), M2, N or RSV virus) | 50                         | 25 (half of the DL)                                   |
| Serum RSV-specific PRNT Strain A
Serum RSV-specific PRNT Strain B  | 20                         | 10 (half of the DL)                                   |
| Serum RSV-specific IgG ELISA  | 63                         | 31.5 (half of the DL)                                 |
| Serum RSV-specific IgA ELISA  | 100                        | 50 (half of the DL)                                   |
| Mucosal RSV-specific IgA ELISA (nasal swabs)  | 2                          | 1 (half of the DL)                                    |
| Serum RSV (strain A) G protein - specific IgG ELISA
Serum RSV (strain B) G protein- specific IgG ELISA   | no detection limit applies | negative reported as 50                               |
| RSV-specific B cell ELISPOT
IgG and IgA   | no detection limit applies | a measured percentage is considered a positive result |

#### **Geometric Mean Titer and Geometric Mean Spot Forming Units**

The Geometric Mean Titer (GMT) and Geometric Mean Spot Forming Units (GMSFU) are calculated by taking the antilogarithm of the mean of the  $\log_{10}$  transformed titers, and Spot Forming Units, respectively.

#### **(Sero)Negative and (Sero)Positive Results**

For each immunogenicity assay a negative result is defined as a titer below the DL, while a positive result is a titer equal to or above the DL.

#### **Response**

For each immunogenicity assay, a response to the vaccine (applicable only for post baseline visits) is defined as either the appearance of a positive result for subjects with a negative result at baseline (Visit 1), or an increase by a factor of at least 2 compared to the Visit 1 for subjects with a positive result at Visit 1. Response status is applicable only for V1b, V2, V3, V3b, V4, EAP Visit, and FU1 and FU2 Visits and is not calculated for subjects with missing Visit 1 titer.

The response rate at each post baseline visit is the percentage of subjects who have a positive response status out of the number of subjects with a non-missing response status (positive or negative) at that visit.

**Responder**

A subject is an ELISPOT Responder to the vaccine in a particular test agent (F pool, G(A) pool, G(B) pool, N pool, M2 pool, RSV Virus) if the subject has a response for at least two post baseline visits (V1b to V 4) within the same test agent. The responder evaluation applies only to subjects with at least two post baseline results available.

The responder rate for each test agent F pool, G(A) pool, G(B) pool, N pool, M2 pool, RSV Virus) is the percentage of subjects who are responders to the relevant test agent out of the number of subjects with a non-missing responder status (positive or negative).

**Individual peak titer**

The individual peak titer is the maximum of titers recorded on V1b, V2, V3, V3b, V4, EAP Visit.

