### 7.1.1 RSV-specific ELISA

RSV-specific IgG/IgA antibody responses will be determined using several ELISAs. Details of the procedure are defined in the SOP [REDACTED] “ELISA to determine RSV-Specific Antibody Titers (IgG) in Human Serum Samples”, SOP [REDACTED] “ELISA to determine RSV-Specific IgA Titers in Human Serum Samples”, SOP [REDACTED] “ELISA to determine RSV G Protein (A-strain) Specific Antibody Titers (IgG) in Human Serum Samples” and SOP [REDACTED] “ELISA to determine RSV G Protein (B1-strain) Specific Antibody Titers (IgG) in Human Serum Samples”.

The individual peak titer is calculated as the maximum of all post baseline titer measurements for that individual. The individual peak titer is only missing if all post baseline titers are missing, otherwise the maximum of the available post baseline titers is used.

The GMT is calculated per visit as well as based on individual peak titers by taking the antilogarithm of the mean of the  $\log_{10}$  titer transformations. The Geometric Mean Fold Increase (GMFI) is calculated analogously per post-baseline visit as the geometric mean of the individual fold increases, i.e. the subjects' post-baseline titers at Visit X, divided by their corresponding baseline titer.

The RSV-specific antibody response rate (applicable only to post-baseline visits) is calculated per visit as well as based on individual peak titers and is defined as the percentage of subjects with antibody response based on the total number of subjects with test results available. The response status is assessed with regard to the corresponding baseline (Visit 1) test result.

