### **Subgroups**

The subgroup consists of 20 subjects per treatment group (a total of 100 subjects) who will have peripheral blood mononuclear cells (PBMC) collection as well as an additional serum and nasal swab sample collection time point one week post each vaccination.

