**Table 2 Treatment Groups**

| Group        | N          | Age [years] | Volume per dose [mL] | 1 st vaccination
Day 0
[Inf.U] | 2 nd vaccination
Day 28
[Inf.U] | Route |
|--------------|------------|-------------|----------------------|---|--|-------|
| 1            | 80         | $\geq 55$   | 0.5                  | $1 \times 10^8$                                 | Placebo  | IM    |
| 2            | 80         | $\geq 55$   | 0.5                  | $1 \times 10^8$                                 | $1 \times 10^8$                                  | IM    |
| 3            | 80         | $\geq 55$   | 0.5                  | $5 \times 10^8$                                 | Placebo  | IM    |
| 4            | 80         | $\geq 55$   | 0.5                  | $5 \times 10^8$                                 | $5 \times 10^8$                                  | IM    |
| 5            | 80         | $\geq 55$   | 0.5                  | Placebo   | Placebo  | IM    |
| Total | 400 |             |                      |   |  |       |

In general, subjects are stratified by age into two groups:  $\geq 55$  to  $< 70$  and  $\geq 70$  years. However, during the staggering phase performed by the staggering site (sentinel cohort and safety cohort) only the younger age group is recruited. In order to have the best power to detect differences between the strata the aim is to achieve equally distributed recruitment across the age strata but at least 20 subjects per treatment group are required in the age stratum  $\geq 70$  years.

The PBMC subgroup consists of 20 subjects per group recruited after the staggering phase. A total of three sites recruit all PBMC subjects.

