Recruitment into the trial is performed in a staggered manner. The staggering process is performed at one clinical trial site. The trial starts with a sentinel cohort with a total of 2 subjects, 1 subject recruited into Group 2 and one subject into Group 4 (i.e. 1:1 subjects receiving Dose 1 and Dose 2). Following a positive safety assessment for the subjects in the sentinel cohort, recruitment in the safety cohort starts. The safety cohort includes a total of 10 subjects, 5 subjects each into Groups 2 and 4 (i.e. 5:5 subjects receiving Dose 1 and Dose 2). Following a positive safety assessment for the subjects in the safety cohort, recruitment in all groups for the remaining subjects is opened. The open recruitment phase includes all treatment groups. The open recruitment phase randomization is stratified by age and site.

PBMC collection is performed in a subgroup of 20 subjects in each treatment group (total of 100 subjects). This subgroup also has an additional serum and nasal swab sample collection time point one week post each vaccination in addition to the serum and nasal swab sample collection time points scheduled for all subjects.

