## Individual peak titer

The individual peak titer is the maximum of titers recorded on V1, V2, V3, V4, and EAP visit from the main study, BV2 and BEAP visit from the booster sub-study. Since V1b, V3b, and BV1b samples are only collected for the PBMC subgroup, they will be excluded from the peak titer selection.

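### The main-study SAP takes the individual peak titer over six scheduled draws in the PBMC subgroup but only four in all other subjects; the effect is small and easily removed

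*SAP*

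**What the plan says.** The main-study SAP (version 1.0, 31 May 2017), General Definitions, reads: "The individual peak titer is the maximum of titers recorded on V1b, V2, V3, V3b, V4, EAP Visit". Section 1.4.2 makes GMT and response rate based on that peak secondary endpoints for the serum IgG, serum IgA, PRNT A, PRNT B and mucosal IgA assays. Section 3.5.7 puts the serum and swab tables on the FAS and PPS, with no separation of subgroup from other subjects.

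The same SAP limits two of the six visits to a subset. Section 1.1 says: "This subgroup also has an additional serum and nasal swab sample collection time point one week post each vaccination". On its size: "PBMC collection is performed in a subgroup of 20 subjects in each treatment group (total of 100 subjects"). On its source: "A total of three sites recruit all PBMC subjects". The schedule in section 2 marks V1b and V3b serum and swabs as subgroup-only, and V2, V3, V4 and EAP as mandatory.

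Two other definitions of the peak exist. Protocol 7.1.1 says: "The individual peak titer is calculated as the maximum of all post baseline titer measurements for that individual"; 7.1.2 and 7.2 say the same, so FU1 and FU2 count there as well. The booster sub-study SAP goes the other way: "Since V1b, V3b, and BV1b samples are only collected for the PBMC subgroup, they will be excluded from the peak titer selection". Section 3.6 of the main-study SAP, which lists departures from the protocol, does not mention the peak.

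**The concern.** A maximum depends on how many values it is taken over. A subgroup subject has up to six chances to reach a high titer or to cross the two-fold response threshold; any other subject has up to four. One summary then combines both kinds of subject, and the two strata are not comparable on it. Because all subgroup subjects come from three sites, the number of draws is also tied to site.

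At stake are the absolute peak GMTs and peak response rates in the main report, and their agreement with the booster report. A PBMC subject who enters the booster sub-study could have one main-study peak under the main SAP and another under the booster SAP.

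**Working it through.** **1. Number of draws, checked against the plan's own figure.** Footnote 5 of the main SAP schedule gives: "Maximal total amount of blood taken/subject: up to 176 mL (642 mL for subjects in the subgroup"). Using the volumes in that footnote:

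- All subjects: 22 (screening) + 4 × 19 (safety lab at V2, V4, FU1, FU2) + 7 × 9 (serum at V1, V2, V3, V4, EAP, FU1, FU2) + 5 × 3 (troponin I) = 176 mL.
- Subgroup: 176 + 7 × 64 (PBMC) + 2 × 9 (serum at V1b and V3b) = 642 mL.

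Both totals are reproduced, and the second needs exactly two extra serum draws. The main SAP peak is therefore over 6 draws (subgroup) or 4 (others). Under the protocol wording, which adds FU1 and FU2, it is 8 or 6.

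**2. Direction.** For any subject, a maximum over six visits is at least the maximum over four of them. No assumption is needed.

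**3. Size: assumptions.** The documents give no within-subject SD per draw. Booster SAP section 4.1 assumes an SD of 0.168 for paired log10 differences; if the errors are independent and equal, the SD per draw is σ = 0.168/√2 = 0.119. True titers are taken as flat across visits. σ is then varied from 0.08 to 0.20.

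**4. Peak GMT.** The expected maximum of k independent standard normal errors is 1.0294 for k = 4 and 1.2672 for k = 6.

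- Subgroup to other subjects: 10^[(1.2672 − 1.0294) × 0.119] = 10^0.0283 = 1.067.
- Pooled group (20 of 80): 10^(0.0283 × 0.25) = 1.016.

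**5. Chance two-fold peak response.** For a subject positive at V1, P = 1 − ∫ φ(y) Φ(y + log10 2/σ)^k dy. At σ = 0.119 this is 11.0% for k = 4 and 14.3% for k = 6. The pooled rise is 0.25 × (14.3 − 11.0) ≈ 0.8 percentage points. A simulation of 1,000,000 subjects agreed (10.9%, 14.3%, GMT ratio 1.067).

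| σ | Subgroup/other peak GMT | Pooled GMT rise | Chance response, 4 draws | 6 draws | Pooled response rise |
|---|---|---|---|---|---|
| 0.08 | 1.045 | 1.1% | 1.4% | 1.9% | 0.1 points |
| 0.119 | 1.067 | 1.6% | 11.0% | 14.3% | 0.8 points |
| 0.15 | 1.086 | 2.1% | 21.1% | 26.5% | 1.4 points |
| 0.20 | 1.116 | 2.8% | 34.6% | 41.7% | 1.8 points |

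**6. If titers are not flat.** At σ = 0.119, if week-1 titers lie 0.1 log10 below the other visits, the subgroup ratio falls to 1.016; if they lie 0.1 above, it rises to 1.193.

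**7. Between arms.** Take the planned 20 subgroup subjects over the vaccinated totals in booster SAP Table 2 (78, 89, 80, 90, 83). The subgroup share runs from 20/90 = 22.2% to 20/78 = 25.6%. The largest distortion of a peak GMT ratio is 10^[0.0283 × (0.256 − 0.222)] = 1.002, or about 0.2% (0.1% to 0.4% over the SD range).

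**8. After the fix.** With V2, V3, V4 and EAP for everyone, the count is 4 against 4, and the chance response rate at σ = 0.119 is 11.0% in both strata.

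**The case against.** The protocol's definition takes every available post-baseline titer and so accepts unequal counts; a genuine peak at one week is then captured, not invented. That is a fair reading of the protocol. It does not make the pooled figure coherent, because three quarters of the planned subjects have no week-1 sample in which such a peak could appear.

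The peak also has a limited role. It is secondary, the planned GMT and fold-increase ratios are by visit, the comparisons are descriptive, and no table title in Appendix 1 names a peak analysis. All of that stands and limits the weight of the point. The peak endpoints are nevertheless listed in section 1.4.2, so the definition will be applied.

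Four stronger readings are tempting, and the documents do not support them:

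- A reader might attribute the whole 11% to 14% chance response to the unequal draws. Most of it comes from taking any maximum, and 11.0% would remain after the fix.
- A reader might infer bias between arms from subgroup shares of 22% to 26%. Those shares divide a planned 20 by vaccinated totals; achieved PBMC numbers are not given. Even so, the distortion is about 0.2% with flat titers. It would grow only if week-1 kinetics differed by dose.
- A reader might cite the Phase I placebo rise in PRNT A from 524 to a peak of 782 (Protocol Table 11). That shows a peak exceeding baseline without vaccine and says nothing about unequal numbers of draws.
- A reader might fear for the primary endpoint. It is the PRNT A GMT two weeks after the last vaccination, uses no peak, and is unaffected, as is the sample size.

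Finally, booster SAP section 1 refers to a main-study SAP Addendum of 11 October 2017. It was not available, and it may have changed the definition.

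**Conclusion.** The point holds on the main-study SAP as supplied. A named secondary endpoint mixes a maximum of six scheduled draws with a maximum of four, and the booster SAP removes the same visits for exactly that reason. The upward direction is certain; the amount is not. It depends on an assumed within-subject SD, independent errors and flat titers, and is sensitive to where week-1 titers lie.

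On those assumptions this is a small distortion of absolute peak summaries, with almost none in between-arm ratios. It merits correction as a matter of definition and consistency; it does not threaten the trial's main conclusions. The undeclared difference from the protocol is a separate defect that does not depend on the size of the effect. Both conclusions are conditional on the addendum not having dealt with the matter.

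**What to change.** First check whether the addendum of 11 October 2017 already changed the definition. If it did not:

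- In the main SAP's peak-titer definition, use V2, V3, V4 and EAP for all subjects. This follows the booster SAP in dropping subgroup-only visits. Do not copy the booster list as it stands, because it includes V1, the pre-vaccination baseline.
- In section 3.6, state that V1b, V3b, FU1 and FU2 are excluded from the peak, contrary to protocol 7.1.1, 7.1.2 and 7.2.
- If the early response is of interest, show a six-visit peak within the IAS only, where all subjects share the same schedule.

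Showing peak response as a difference from Group 5 with a 95% CI is an optional extra; it addresses the general effect of taking a maximum, not the unequal draws.

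The cost is a wording change and one derivation. Booster SAP section 2.2.2 records that the main study has been unblinded, so a change made now should be documented as such. The downside is that a true one-week peak in a subgroup subject no longer counts towards the peak, though it remains in the by-visit tables.
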